## 2 Schedule of Study Assessments\*

Procedure	Screening	Cycle 1			Cycle 2	Cycle 3 	Cycle 4 and higher 	Discontinuation From Study Drug	30 Days (+/- 7 days) following last dose of study drug 	Follow-Up Phase
	≤ 28 days from Baseline (First day study drug administration)	Day	Day	Day						
		1 	8 	15 	Day	1 	1 	1		Every 3 months
Informed Consent	X									
Reconfirm Eligibility			X							
Medical history (including signs/symptoms/diagnoses)	X									
Record prior medications, treatments	X									
Record prior anti-cancer therapies	X									
Physical examination, vital signs, weight	X				X	X	X 	X	X	
Transfusion History	X	X 			X	X	X	X	X	
ECOG performance status	X				X	X	X 	X	X	
Bone marrow biopsy and aspirate 	X 							X 		
ECG	X							X		
Hematology 	X	X	X	X	X	X 	X 	X 	X 	X 
Serum chemistry 	X	X	X	X	X	X 	X 	X 	X 	X 
MDS-specific tests (Serum B12, erythropoietin)	X									
TSH 	X						X 	X 		
Pregnancy testing 	X 	X	X	X	X	X 	X 	X 	X 	X 
Register patient into RevAssist® program	X									
Prescribe lenalidomide via RevAssist® 		X 				X 	X 	X 	X 	
Record adverse events	X	X 	X	X	X	X	X	X 	X	X
Record concomitant therapies/procedures		X 	X	X	X	X	X	X 	X	X
Obtain Follow-Up anti-cancer treatments										X
Obtain Follow-Up survival information										X

\*Variations of ± 3 days of the scheduled visit are permitted during Cycles 1 to 3, and ± 7 days of scheduled visits are permitted thereafter.

An unscheduled visit can occur at any time during the study. Source must be maintained for these unscheduled visits. The date for the visit and any data generated must be recorded on the appropriate CRF.

Include testing for expression assays. Within 6 weeks of starting therapy.

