**Initial microarray data was available on 8 responders and 8 non-responders who did not have the del(5q). (the “training” set).** There was a very distinct pattern of gene expression that separated the responders from non-responders. Equally exciting was the observation that among the 100 ranked genes of interest in the heat-map were groups of genes that have previously been shown to be associated with MDS pathology. It seems that a number of genes involved in erythropoiesis are clearly under-expressed in patients, including all of the responders. For example HBA1 (alpha1 globin), ankyrin1 erythrocytic, dematin or EPB 49 (erythrocyte membrane protein band 49), EPB3 (red cell anion exchanger), ferrochelatase, hemoglobin alpha 2/DEF (human alpha globin gene with flanks), human sickle cell beta globin, Kidd blood group (SLC14A1) are genes that are under-expressed in the cells of the responders. This expression signature can be used for predicting which patients have a chance to respond versus those who definitely will not benefit. However, the DNA microarray technology cannot be easily adapted for prospective clinical testing in a timely fashion. Two simpler assays to measure gene expression currently used by

clinical labs are quantitative real time PCR and the Luminex bead hybridization assay. The relative ease of use and cost of these assays will allow them to be easily implemented in a clinical setting in the future. This bead based technology is being rapidly developed for clinical, research and diagnostic purposes. It is less complex than microarray analysis, and can analyze the expression of up to a hundred genes in a single well, making it easier to use in the clinical diagnostic setting. The results with the Luminex assay gave essentially the same results as the Affymetrix chips, and better results than the TaqMan. Identical methodology for analysis of Affymetrix, TaqMan qPCR and Luminex data were used. Thus Luminex **may** be adaptable to the broader clinical setting.

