## **6 Investigational Plan**

### **6.1 Overall design**

#### **6.1.1 PRE, INTRA, and POST-THERAPY STUDIES:**

- Bone marrow (BM) aspirate and biopsy
  - All patients must have a BM aspirate and biopsy examination performed within 6 weeks before starting therapy. Routine diagnostic studies include morphology, histochemistry, flow cytometry, immuno-phenotyping, karyotyping, fluorescence in situ hybridization (FISH), cytogenetics. A marrow sample will be saved for the gene

- expression microarray, Luminex bead assay, and real-time PCR.
- A repeat bone marrow aspirate and biopsy will be done at discontinuation from study drug to document complete response, if needed.
  - **Medical/Medication History:** Obtained at screening. Medical history to include diagnoses and any signs/symptoms within prior 28 days. Medication history within prior 28 days and all prior treatment for MDS.
  - **Physical Exam:** Screening, monthly at Day 1 of Cycles 2, 3, and 4 and at Day 1 of every other cycle thereafter, and at discontinuation from study drug, and 30 days (+/- 7 days) following the last dose of study drug.
  - **ECOG Status:** At screening, Day 1 of Cycles 2, 3, and 4, and every other cycle thereafter.
  - **Transfusion History:** Screening, monthly at Day 1 of Cycles 1, 2, 3, each Day 1 study visit thereafter, at discontinuation from study drug, and 30 days (+/- 7 days) following the last dose of study drug.
  - **Hematology** (hemoglobin, hematocrit, RBC indices: RBC count, mean cell volume, mean cell hemoglobin, mean cell hemoglobin concentration; WBC count with differential; and platelet count) at screening, weekly during cycles 1 to 3, and then monthly (i.e., at Day 1 of each cycle) thereafter, at discontinuation from study drug, and 30 days (+/- 7 days) following the last dose of study drug.
  - **Clinical Chemistry** (creatinine, BUN, total bilirubin, alkaline phosphatase, ALT, AST, LDH, total protein) at screening, on Cycle 1 Day 1 and Cycle 1 Day 15 and on Day 1 of Cycles 2, 3, 4 and then as clinically indicated after cycle 4, at discontinuation from study drug, and 30 days (+/- 7 days) following the last dose of study drug. Thyroid stimulating hormone (TSH) will be done at screening Cycle 4 and then every 16 weeks (i.e., Cycles 8, 11, 16, etc.), and at discontinuation from study drug. T3 and T4 levels may be assessed as clinically indicated.

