## **6.2 Screening and Eligibility**

The Investigator is responsible for keeping a record of all subjects who sign an Informed Consent Form for entry into the study. All subjects will be screened for eligibility. Screening procedures are outlined in Section 2, Schedule of Study Assessments and unless otherwise specified, must take place within 28 days prior to initiation of therapy.

Approximately 56 of subjects with transfusion-dependent, **non-del(5q)** low/Intermediate-1 risk Myelodysplastic Syndrome will be screened for enrollment and must meet the eligibility criteria below.

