#### **Inclusion criteria**

1. Understand and voluntarily sign an informed consent form.

2. Age  $\geq$  21 years at the time of signing the informed consent form.
  3. Able to adhere to the study visit schedule and other protocol requirements.
  4. A confirmed diagnosis (using standard FAB criteria) of a myelodysplastic syndrome with low/Int-1 risk and with a non-del(5q) karyotype must be established.
  5. Patients must have transfusion dependence (at least 2 units within 8 weeks prior to starting therapy).
  6. All transfusion dependent **non**-del(5q) low/Int-1 risk patients will be eligible for treatment with Revlimid®
  7. Newly diagnosed as well as previously treated patients will be eligible
  8. Patients with primary de novo or secondary MDS will be eligible
  9. All previous cancer therapy, including radiation, hormonal therapy and surgery, must have been discontinued at least 4 weeks prior to treatment in this study.
10. ECOG performance status of 0-2 at study entry (see Appendix II).
11. Laboratory test results within these ranges:
- Absolute neutrophil count  $> 250/\mu\text{L}$
  - Platelet count  $> 30,000/\mu\text{L}$
  - Serum creatinine  $\leq 2.0 \text{ mg/dL}$
  - Total bilirubin  $\leq 1.5 \text{ mg/dL}$
  - AST (SGOT) and ALT (SGPT)  $\leq 3 \times \text{ULN}$
  - BUN  $\leq 2 \times \text{ULN}$
12. Disease free of prior malignancies for  $\geq 2$  years with exception of currently treated basal cell, squamous cell carcinoma of the skin, or carcinoma "in situ" of the cervix or breast.
13. All study participants must be registered into the mandatory RevAssist® program, and be willing and able to comply with the requirements of RevAssist®.

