### **6.2.2 Exclusion criteria**

1. Any serious medical condition, laboratory abnormality, or psychiatric illness that would prevent the subject from signing the informed consent form.
2. Pregnant or breast feeding females. (Lactating females must agree not to breast feed while taking lenalidomide).
3. Any condition, including the presence of laboratory abnormalities, which places the subject at unacceptable risk if he/she were to participate in the study or confounds the ability to interpret data from the study.
4. Any clinically significant cardiac disease, including congestive heart failure
5. Liver function studies including SGOT/SGPT > 3 x ULN
6. Clinically significant renal disease.
7. Any previous chemotherapy, hematopoietic growth factors, erythropoietin, or cytokines within 4 weeks of starting treatment. Note: prior therapy with G-CSF within 4 weeks is allowed.
8. Use of any other experimental drug or therapy within 28 days of baseline.
9. Known hypersensitivity to thalidomide.
10. The development of erythema nodosum if characterized by a desquamating rash while taking thalidomide or similar drugs.

---

† A female of childbearing potential is a sexually mature woman who: 1) has not undergone a hysterectomy or bilateral oophorectomy; or 2) has not been naturally postmenopausal for at least 24 consecutive months (i.e., has had menses at any time in the preceding 24 consecutive months).

11. Any prior use of lenalidomide. (Patients with prior therapy with thalidomide will be eligible as long as at least 4 weeks have elapsed between end of the drug and accrual on the present trial)
12. Concurrent use of other anti-cancer agents or treatments.
13. Known positive for HIV or infectious hepatitis, type B or C.
14. Life expectancy < 3 months

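### The expression marrow may be drawn up to 14 days before the 4-week washout begins, so the primary biomarker can be measured while the patient is on prior therapy

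*Combined protocol and SAP*

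**What the plan says.** **Sample timing.** Section 6.1.1: "All patients must have a BM aspirate and biopsy examination performed within 6 weeks before starting therapy". Part of that marrow is kept for the microarray, Luminex and PCR assays. Footnote 1 to the schedule in Section 2 says the same of the expression sample: "Include testing for expression assays. Within 6 weeks of starting therapy".

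**Washout.** Exclusion criterion 7 (Section 6.2.2) bars "Any previous chemotherapy, hematopoietic growth factors, erythropoietin, or cytokines within 4 weeks of starting treatment", and then adds "Note: prior therapy with G-CSF within 4 weeks is allowed". Inclusion criterion 9 says that other cancer therapy "must have been discontinued at least 4 weeks prior to treatment in this study". Exclusion criterion 11 handles thalidomide separately: its 4 weeks run to accrual on the trial, not to the first dose.

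**Population.** Inclusion criterion 7: "Newly diagnosed as well as previously treated patients will be eligible".

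**Role of the sample.** The primary endpoint (Section 5.2.1) is the pre-therapy expression profile. The primary objective (Section 5.1.1) is to confirm the signature's predictive value and to set z-score boundaries for selecting patients in later studies. Section 4.8 describes the signature: "It seems that a number of genes involved in erythropoiesis are clearly under-expressed in patients, including all of the responders".

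**The concern.** The washout protects the start of treatment, but the primary endpoint is measured earlier, at the marrow draw, and no washout is tied to the draw. As the protocol uses the term, pre-therapy means before lenalidomide; it does not mean free of other treatment.

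The signature is low expression of erythropoiesis genes in responders. An erythroid growth factor or a cytotoxic drug could plausibly alter that reading. The protocol guards a clinical outcome against the same influence: the hemoglobin criterion for complete remission in Section 8.3 counts only in a patient who is untransfused and not on erythropoietin. The biomarker has no matching safeguard.

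At stake are the classification of individual patients and the z-score boundary that the trial is meant to hand on. All three assays use the pre-therapy marrow, so agreement between them would not reveal a profile altered by another drug. The boundary will also rest on few responders: if the 26% transfusion-independence rate quoted from MDS-002 carried over (an assumption), 56 × 0.26 = 14.6, or about 15.

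**Working it through.** The plan gives no figure of its own on this point, so the check compares the time windows and then looks for any rule that closes the gap.

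**1. Overlap.** Both periods have the same anchor, the first dose of lenalidomide.

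- Marrow window (Section 6.1.1; Section 2, footnote 1): 6 × 7 = 42 days, so day −42 to the first dose.
- Washout (exclusion 7; inclusion 9): 4 × 7 = 28 days, so prior therapy may continue until about day −28.
- Overlap: 42 − 28 = 14 days.
- Share of the permitted window: 14/42 = one third. This is a share of days. It is not a share of patients, because the documents do not say when within the window marrows will be drawn.

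**2. Agents.**

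- Chemotherapy, erythropoietin, other growth factors, cytokines and other cancer therapy: the 14-day overlap applies.
- G-CSF: exempt from the washout, so exposure at the draw is possible anywhere in the 42 days.
- Thalidomide: if accrual precedes the draw, its 4 weeks have already passed and there is no overlap.

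**3. Rules that might close the gap.**

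- Section 6.2 says that screening procedures "must take place within 28 days prior to initiation of therapy", but only where nothing else is specified. For the marrow, 6 weeks is specified, twice and consistently.
- Exclusion 3 covers conditions that confound interpretation of the data. It is discretionary and does not mention when the marrow is taken.
- Section 11 has no rule to flag, exclude or adjust for samples taken on prior treatment.

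**4. What cannot be calculated.** A change in sensitivity or specificity needs at least two inputs: the fraction of samples drawn on such a therapy, and the fraction of those whose classification changes as a result. The documents give neither. If either is zero, there is no effect. Direction is open too: a responder misread as negative lowers sensitivity, a non-responder misread as positive lowers specificity, and erythroid stimulants and cytotoxic drugs need not act the same way.

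**5. After the change below.** For planned draws, the on-therapy overlap for the agents with a 4-week washout falls from 14 days to 0. G-CSF exposure and carry-over from a recent last dose remain possible and have to be handled by flagging.

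**The case against.** The strongest reply is that the consent rules narrow the gap. Section 6.1.1.2 allows no study procedure before consent, and the schedule places consent in the screening column headed 28 days or less from baseline. On that reading, a marrow drawn for the study falls after the washout has begun, and the earlier 14 days concern mainly marrows taken beforehand for routine care. This has weight, but it does not close the gap. Footnote 1 gives the expression sample its own 6 weeks, earlier consent is not expressly barred, and a routine marrow used for the assays is still the primary measurement.

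The second reply is that no section says erythropoietin or chemotherapy shifts the signature, by how much, or for how long. That stands: the effect is plausible, not documented.

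The third is that affected samples could be traced already, because all prior MDS treatment is recorded (Section 6.1.1) and the schedule collects prior medications and anti-cancer therapies. That is largely true. However, no analysis uses this information, and the documents do not say that last-dose dates are captured against the draw date.

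The fourth is that a draw just after the last dose satisfies a simple after-the-last-dose rule while carry-over may be greatest. This also stands, and it is why the fix pairs the timing rule with a flag for samples drawn shortly after prior therapy.

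**Conclusion.** The timing gap is real: 14 of 42 permitted days, one third of the window, in which the primary biomarker can be measured on therapy that the protocol requires to be stopped before lenalidomide. This rests only on the stated windows and their common anchor.

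A reader might go further and discount the 94% sensitivity quoted in Section 11.1 by an assumed share of affected responders. The documents do not support such a figure. It would require draws spread evenly over the 6 weeks, an assumed rate of prior treatment among early draws, and every affected responder reading negative. Nor do the documents support listing thalidomide among the clearly affected drugs.

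The point is therefore an inexpensive safeguard against plausible confounding of unknown frequency, size and direction. It is not a demonstrated bias.

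**What to change.** Reconcile the marrow window with the washout passages, leaving the washout lengths as they are.

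1. In Section 6.1.1 and in footnote 1 of the schedule, state that the one planned expression sample is drawn, within the existing window, after the last dose of the therapies subject to the 4-week washout.
2. Record the last-dose date of each such therapy, and of G-CSF, alongside the draw date.
3. Do not repeat a marrow that already exists from an earlier date. Flag any sample drawn on or shortly after prior therapy, including G-CSF. The sponsor should define in advance what counts as shortly after.
4. In Section 11, pre-specify a sensitivity analysis of the signature and the z-score boundary without the flagged samples. Fixing it now matters, because an exclusion chosen once responses are known could itself bias the boundary.

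The cost is a sentence in each of two places, two date fields, one extra analysis, and slightly tighter scheduling for patients coming off prior therapy. No extra marrow is needed, and eligibility and treatment do not change.

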Subject will follow this schedule if determined to have a response after the first 12 weeks of treatment for subsequent visits.

To document complete response, as needed.

Performed every other cycle starting at Cycle 4 (i.e., Cycles 4, 6, 8, 10, etc.)

[figure not shown]
After cycle 4, subjects may have Day 1 evaluations of odd number cycles performed by their local oncologist. Day 1 of even numbered cycles must be performed at Columbia University Medical Center.

After cycle 4, perform only as clinically indicated

 Subjects who do not reside locally, may have this visit performed by their local oncologist

Cycle 2 Day 1, Cycle 3 Day 1, and Cycle 4 Day 1 visits must be performed at Columbia University Medical Center. Other visits during Cycles 2 and 3 may be performed by subject's local oncologist.

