### 3 Schema:

All responders should continue therapy until disease progression

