  - All study participants must be registered into the mandatory RevAssist® program, and be willing and able to comply with the requirements of RevAssist®.

- Pregnancy test for women: Females of childbearing potential (FCBP)† must have a negative serum or urine pregnancy test with a sensitivity of at least 50 mIU/mL within 10 – 14 days prior to and again within 24 hours of prescribing lenalidomide. FCBP with regular or no menstruation must have a pregnancy test weekly for the first 28 days and then every 28 days while on therapy (including breaks in therapy), at discontinuation of lenalidomide and at Day 28 post the last dose of lenalidomide. Females with irregular menstruation must have a pregnancy test weekly for the first 28 days and then every 14 days while on therapy (including breaks in therapy), at discontinuation of lenalidomide and at Day 14 and Day 28 post the last dose of lenalidomide (see Appendix I: Risks of Fetal Exposure, Pregnancy Testing Guidelines and Acceptable Birth Control Methods).
- 12-Lead EKG will be performed prior to therapy.
- **MDS-Specific Tests:** at baseline and as clinically appropriate thereafter (serum B12 and erythropoietin). Optional depending on clinical situation: serum iron, total iron-binding capacity (TIBC), ferritin; flow cytometry for CD34.
- **Adverse Events, Toxicity, Concomitant Medications/Procedures:** at each study visits per Schedule of Study Assessments (Section 2), assessed by NCI Common Terminology Criteria for Adverse Events, Ver.3 Note: After Cycle 4, these assessments will be obtained every 8 weeks.
- Patient blood counts, chemistries, transfusion requirements will be reviewed at 4-week intervals with decision for continued therapy at week 12. At the discretion of the Principal Investigator, therapy will be discontinued in the event of a serious adverse event.
- Transfusion criteria: Packed red blood cells (PRBC) will be transfused in case hemoglobin falls below 8.0 Gm/dL or at a higher level in a symptomatic patient. Platelet transfusions will be given only if the patient is showing evidence of bleeding or if at risk of bleeding.

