### **6.1.1.3**

The starting dose of REVLIMID® will be 10 mg days 1-28 with the first dose reduction going to 5 mg days 1-28 of a 28 day cycle. Therapy will cease if there is no response after 12 weeks. Patients responding to treatment will continue on Revlimid® until disease progression or unmanageable toxicities.

- Based on previous trials in del 5q MDS patient one hundred percent of patients reported at least one adverse event; 89% (131/148) experienced at least one grade 3/4 adverse event. Eighty percent required a dose delay and/or reduction for toxicity during the study. Thirty-four percent required a second dose delay/reduction. Dose adjustment recommendations for neutropenia and thrombocytopenia are provided in product labeling. Patients should have complete blood counts monitored weekly for the initial 12 weeks and at least monthly thereafter. Thromboembolic events were rare in the Revlimid® studies in MDS patients with deletion 5q cytogenetic abnormalities. However, in recently reported trials conducted in multiple myeloma, a significantly increased risk of deep venous thrombosis and pulmonary embolism was observed in patients treated with Revlimid® combination therapy. An elevated risk of thrombosis has also been reported when erythropoietin is used during Revlimid® treatment. The role of prophylactic anticoagulation and/or antiplatelet therapy with Revlimid® has not been adequately assessed. Any prophylactic measures should be prescribed after a careful assessment of individual risk factors.
- Patients with serum creatinine above 2.5 mg/dl were excluded from the studies. Because Revlimid® is predominately excreted by the kidney, renal function should be carefully monitored.
- Females should be advised to avoid pregnancy while taking Revlimid®. Revlimid is an analogue of thalidomide, a known human teratogen that causes severe human birth defects. Additional

reproductive toxicity studies will be performed to assess any potential Revlimid® teratogenicity. Only prescribers and pharmacists registered under the RevAssist® program can prescribe or dispense Revlimid®. Patients must agree to comply with the RevAssist® program requirements.

[figure not shown]

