## **6.7 Discontinuation of Study Treatment**

Treatment will continue for 12 weeks of treatment or the occurrence of any of the following events.

- Disease progression as defined by IWG
- Adverse event(s) that, in the judgment of the Investigator, may cause severe or permanent harm or which rule out continuation of the treatment regimen.
- Toxicity that delays the start of the next cycle by more than 4 weeks.
- Discontinuation of lenalidomide for any reason.
- Major violation of the study protocol.
- Withdrawal of consent

- Lost to follow up
- Death
- Suspected pregnancy

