**8.6 Disease transformation:**

Transformation to AML, 20% or more blasts.

**8.7 Cytogenetic response:** Requires 20 analyzable metaphases using conventional cytogenetic techniques.

**Complete:** No detectable cytogenetic abnormality, if pre-existing abnormality was present.

**Partial:** 50% or more reduction in abnormal metaphases.

**8.8 Pre-therapy assessments:** Baseline complete blood count (CBC) to which improvements will be compared was standardized using a mean value of the 4 weeks prior to the start of therapy for all patients.

**8.9 During therapy:** Responses will be assessed at 12 weeks of therapy. With regard to packed red blood cell transfusions (PRBC) and transfusion independence, the same 4 week time period was used prior to treatment to determine transfusion dependence and to obtain a baseline monthly requirement. Subsequent transfusions will be reviewed at 16 weeks, and 1-year time points.

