### 11.2 Analysis of Clinical Response

- Response will be evaluated **every 4 weeks during the first 12 weeks** of therapy for each of the 56 transfusion-dependent low/Int-1 risk MDS patients. Treatment will be stopped and the patient will be taken off the protocol in case of no response or stable disease by 12 weeks. International Working Group (**IWG 2006**) **criteria** will be used for response evaluation. The proportion of TI will be calculated and an exact 95% confidence interval of TI proportion will be estimated. The percent of major and minor responses in erythroid,

platelets, neutrophils, bone marrow and cytogenetic will also be calculated as the secondary endpoints.

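### Section 11.2 plans percent marrow and cytogenetic responses, but the only repeat marrow is as-needed, at drug discontinuation and for complete response only, so the percentages would be selected and mistimed

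*Combined protocol and SAP*

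**What the plan says.** **Repeat marrow.** Section 6.1.1 provides: "A repeat bone marrow aspirate and biopsy will be done at discontinuation from study drug to document complete response, if needed". In the Section 2 schedule, the marrow row has one entry after screening, with footnote 10: "To document complete response, as needed".

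**When drug stops.** Section 6.1.1.3 says: "Patients responding to treatment will continue on Revlimid® until disease progression or unmanageable toxicities". The Synopsis agrees, and Section 3 has: "All responders should continue therapy until disease progression". Section 6.7 is worded differently: "Treatment will continue for 12 weeks of treatment or the occurrence of any of the following events". Its list includes consent withdrawal, a major protocol violation and suspected pregnancy as well as progression and toxicity.

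**When response is judged.** Section 8.9 says: "Responses will be assessed at 12 weeks of therapy". The inputs to that decision, in Section 6.1.1, do not include marrow: "Patient blood counts, chemistries, transfusion requirements will be reviewed at 4-week intervals with decision for continued therapy at week 12".

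**What is reported.** Section 11.2 extends the list of percentages beyond erythroid, platelet and neutrophil responses: "bone marrow and cytogenetic will also be calculated as the secondary endpoints". The Synopsis and Section 5.2.2 list only the first three. Sections 5.1.2 and 8.2 name the remaining IWG criteria as secondary efficacy parameters.

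**The concern.** CR, PR, marrow CR and cytogenetic response (Sections 8.3, 8.4 and 8.7) all need a marrow taken on study. The plan ties its only such marrow to the end of treatment and to one of these four categories. For a responder, the end of treatment is usually the point at which the response has ended or the drug is no longer tolerated.

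Section 11.2 names no denominator. A percentage over all 56 treats a patient who was never re-examined as a non-responder. A percentage over those examined describes whoever was judged to need a marrow, and the protocol does not define that need. Neither is a response rate in the treated population, and a reader of the trial report could not tell which had been used.

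**Working it through.** The plan states no figure for these endpoints, so there is none to reproduce. The check sets the definitions against the sampling, then uses the earlier non-del(5q) trial in Section 4.7 to illustrate timing and size.

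**1. Does the planned sample serve each response category?**

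- CR (8.3): needs a repeat marrow, with an eight-week duration attached to the marrow finding. Section 8.10 also requires two consecutive determinations a week or more apart. The planned marrow is for this category, but it supplies one determination and cannot show duration.
- PR (8.4): needs a measured fall in marrow blasts, and 8.10 applies. No planned sample.
- Marrow CR (listed after 8.4): needs a measured fall in marrow blasts. No planned sample.
- Cytogenetic response (8.7): needs 20 analyzable metaphases. No planned sample.

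**2. When would the discontinuation marrow fall?**

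Section 4.7 gives a median of 5 weeks to response and a median duration of 41.0 weeks.

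- Responders continue as in the Synopsis, Section 3 and 6.1.1.3: 5 + 41 = week 46. The lag after the week-12 assessment is 46 − 12 = 34 weeks. This adds two medians, so it shows the order of magnitude for a typical responder and is not an estimate.
- Section 6.7 read literally: discontinuation at week 12, so no lag.

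The timing therefore depends on which text governs, and the document does not settle it.

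**3. How many patients are involved?**

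Inputs from Section 4.7: 214 treated, 47 with an abnormal karyotype, 9 of those with a cytogenetic response, 4 complete.

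- Proportion with an abnormal karyotype: 47/214 = 22.0%. Expected here: 56 × 47/214 = 12.3.
- Cytogenetic response among those: 9/47 = 19.1%. Expected here: 56 × 9/214 = 2.4, of which complete 56 × 4/214 = 1.0.

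These assume that the earlier rates carry over to the 56 patients planned here.

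**4. What does the choice of denominator do?**

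In the earlier trial the same nine responders are 9/47 = 19.1% of those with an abnormal karyotype and 9/214 = 4.2% of all treated. That gap arises with no missed response. Unexamined patients counted as non-responders would lower the figure further, by an amount that depends on how many marrows are taken and when. The documents give neither.

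**The case against.** The strongest reply is that the discontinuation marrow is not always too late. Section 6.7 lets patients stop for reasons unrelated to response, and read literally it puts discontinuation at week 12. A stop for toxicity need not end a marrow or cytogenetic response. Progression under Section 8.5 can be worsening cytopenias alone, which does not show that a cytogenetic response was lost. All of this stands. A reader might infer that these responses cannot be measured at all, that the rates would be near zero, or that most responses would be missed. The documents do not support that: the expected 2 to 3 cytogenetic responders is a count of responders, not of those missed.

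A reader might also infer that patients stopped at week 12 have nothing to document. That is wrong under Section 8. Marrow CR and cytogenetic response carry no blood-count or transfusion condition, so a patient stopped for no response or stable disease could meet either. The point then cuts the other way, because the planned marrow is not for those categories and such a patient need not be sampled.

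These endpoints are also peripheral. The plan proposes no comparison with the earlier 19%, and even ideal sampling would be imprecise: 2 of 12 has an exact 95% interval of about 2% to 48%. This limits the importance of the problem but does not remove it, since Section 11.2 still commits to the percentages.

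Unscheduled visits are allowed, so an on-treatment marrow is possible. None is planned for this purpose, and ad hoc sampling would add to the selection.

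The graphic in Section 3 could not be read. That there is only one repeat marrow rests on Sections 2 and 6.1.1, which agree.

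**Conclusion.** The mismatch is real and confined to secondary endpoints. Followed as written, the plan gives marrow and cytogenetic percentages that rest on a selected and often mistimed subset, or that silently count unexamined patients as non-responders. Even with Section 6.7 read literally, so that timing is no longer the problem, the marrow stays optional, limited to CR and unconfirmed.

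The size of the error cannot be computed. What can be said, if the earlier trial's rates hold, is that about 12 patients would be informative for cytogenetics and 2 to 3 would respond, so one or two unsampled or mistimed patients would change the result materially.

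The primary endpoint uses the pre-therapy marrow, and transfusion independence and hematologic improvement use transfusions and blood counts. None of these is affected.

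**What to change.** **Section 11.2 (the essential change).** Report marrow and cytogenetic responses only as descriptive counts among patients with a paired on-study marrow and, for cytogenetics, an abnormal baseline karyotype. Show the denominator and the time of each marrow. Alternatively, delete them from the percent list, which would bring 11.2 into line with the Synopsis and Section 5.2.2. In that case add a sentence to 5.1.2 and 8.2 saying which of the remaining IWG criteria the planned sampling cannot assess.

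**Sections 2 and 6.1.1.** Let the same as-needed marrow be taken when on-drug blood counts first meet the CR criteria rather than at discontinuation, and state that it serves CR only. This does not rescue PR, marrow CR or cytogenetic response, because patients who reach those without CR-level counts would still not be sampled. It also remains a single marrow, so a CR documented this way should be reported as resting on one determination.

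**Section 6.7.** Reconcile it with the Synopsis, Section 3 and 6.1.1.3 on how long responders are treated, since the timing of any discontinuation marrow depends on it.

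**Cost.** Wording changes only; an already planned procedure moves and none is added. The downside is that these endpoints become descriptive.
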